The starting dose of ASP2215 in the dose-evaluation part is 120 mg. According to the Table, at least 3 subjects will receive ASP2215 at the assigned dose (120 mg, or 80 mg as necessary) for the determination of MTD and/or RED. The DLT assessment period for the dose-evaluation part is until the end of induction therapy Cycle 1 and until the end of consolidation therapy Cycle 1 for the dose-expansion part. Subjects who meet any of the

following criteria will be considered unevaluable for DLT and will be replaced by another subject in the cohort.

- A subject that receives less than 80% of the assigned dose of ASP2215 during DLT assessment period specified in each part (e.g., subject in dose assessment part who misses ≥ 3 daily doses during DLT assessment period of dose evaluation part and interrupts the study for a reason other than a DLT)
- Unable to assess the safety adequately during DLT assessment period specified in each part such as due to the lack of required safety assessment(s)

The decision of whether or not to proceed to the next dose of ASP2215 will be made through discussion among the sponsor, principal investigators, and medical advisor with reference to the recommended dose level calculated using Bayesian-CRM, the safety data, etc., and after review by the sponsor's responsible person. The MTD is defined as the highest dose of ASP2215 at which the posterior mean of the DLT incidence during Cycle 1 of induction therapy is estimated to be closest to 33%.

[Phase 2 part]

After achieving the objectives of the Phase 1 part, the Phase 2 part can be initiated. Subjects will receive ASP2215 at the recommended dose established in the Phase 1 part. The primary objective of the Phase 2 part is to evaluate the efficacy of ASP2215 in combination with induction therapy in newly diagnosed FLT3-mutated AML subjects. The target population will be limited to newly diagnosed FLT3-mutated AML. The primary analysis for the primary endpoint of the CR rate will be conducted when all registered subjects complete the induction therapy period.

After treatment discontinuation, subjects will have a 30-day follow-up visit for safety, after which the subjects will enter the long-term follow-up period for collection of subsequent AML treatment, remission status, relapse and survival (cause and date of death). Duration of long-term follow-up is until 3 years after the last subject first treatment or completion of 30-day follow-up of the last subject, whichever is longer.

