6 ANALYSIS VARIABLES

6.1 Efficacy Endpoints

6.1.1 Response Definition

Antitumor response will be assessed on the days of bone marrow sampling based on the bone marrow findings, and peripheral blast count, neutrophil count, and platelet count. Preferably, samples from both bone marrow aspiration and biopsy should be obtained, but if the bone marrow aspiration was determined to be sufficient, biopsy may be omitted.

Antitumor response is defined per modified Cheson criteria (2003) or modified ELN recommendations (2017) as outlined below [Döhner et al, 2017; Cheson et al, 2003].

[Phase 1 part]

The assessment will be performed by the investigator. The results of bone marrow findings and peripheral blast count will be entered into the eCRF.

[Phase 2 part]

Bone marrow aspiration and/or biopsy samples and hematology samples are evaluated both centrally and locally. If bone marrow samples were obtained for unscheduled visits, those samples along with hematology samples should be submitted for central assessment.

Definitions

Complete Remission (CR):

CR is defined as a morphologically leukemia-free state at the post-baseline visit, having a neutrophil count of $\geq 1,000/\text{mm}^3$ and platelet count of $\geq 100,000/\text{mm}^3$, bone marrow myeloblasts $< 5\%$. There must be no evidence of Auer rods and no evidence of extramedullary leukemia. The blast counts in peripheral blood must be $\leq 2\%$.

Complete Remission with Partial Hematologic Recovery (CRh):

CRh is defined as a condition at the post baseline visit, having bone marrow myeloblasts $< 5\%$, partial hematologic recovery neutrophil count $\geq 500/\text{mm}^3$ and platelet count $\geq 50,000/\text{mm}^3$, no evidence of extramedullary leukemia and cannot be classified as CR. The blast counts in peripheral blood must be $\leq 2\%$.

Complete Remission with Incomplete Platelet Recovery (CRp):

CRp is defined as a condition that meets all of the CR criteria at the post-baseline visit, except for the unrecovered platelet count ($< 100,000/\text{mm}^3$).

Complete Remission with Incomplete Hematological Recovery (CRi):

CRi is defined as a condition that meets all of the CR criteria at the post-baseline visit, except for the unrecovered neutrophil count ($< 1,000/\text{mm}^3$) whether or not having unrecovered platelet counts).

Partial Remission (PR):

At a post-baseline visit, PR is defined as a condition with regeneration of normal hematopoietic cells in the bone marrow.

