6.1.3 Secondary Efficacy Endpoints

[Phase 1 part]

Not applicable.

[Phase 2 part]

- Overall survival (OS)

OS is defined as the time from start date of the first treatment until the date of death due to any cause. For a subject who is not known to have died by the end of long-term follow-up, OS is censored at the date of last known alive.

As a sensitivity analysis, OS is defined similarly as the above, however, subjects who undergo HSCT will be censored at the time of HSCT.

- Event free survival (EFS)

The time from the date of start date of the first treatment until the date of documented relapse after CR, treatment failure or death from any cause, whichever occurs first. For a subject with none of these events, EFS is censored at the date of last disease assessment. Subject without post-treatment disease assessment will be censored at the start date of the treatment.

Treatment failure includes those subjects who failed to achieve CRc by the end of consolidation period, or who discontinued the treatment due to “lack of efficacy” without a previous response.

Treatment failure date refers to the end of treatment date for subjects with treatment failure.

- Relapse free survival (RFS)

The time from the date of achievement of first CRc until relapse or death from any cause, whichever comes first for subjects who achieve CRc. For a subject who is not known to have relapsed or died, RFS is censored on the date of last relapse-free disease assessment date.

Last relapse-free disease assessment date refers to the subject’s last disease assessment date.

- CR rate after each treatment therapy

Defined as the number of subjects who achieve the best response of CR divided by the number of subjects in the analysis population after each treatment therapy period.

Subjects with unknown or missing response, or who provide no information on response will be treated as non-responders and will be included in the denominator when calculating rates.

- CR rate without MRD after each treatment therapy

Defined similarly as CR rate after each treatment therapy. Responders achieve that the best response is CR and MRD status is negative. CRc rate without MRD after each treatment therapy will also be defined similarly.

- CRh rate after each treatment therapy

Defined similarly as CR rate after each treatment therapy.

- CRc (Composite CR) rate after each treatment therapy

CRc: CR + CRp + CRi

Defined similarly as CR rate after each treatment therapy.

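### RFS and EFS count events found in long-term follow-up but censor event-free subjects at an undefined last disease assessment; if follow-up contacts do not count, Kaplan-Meier RFS is biased downward

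*SAP*

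**What the plan says.** **Events (SAP 6.1.3).** RFS is "The time from the date of achievement of first CRc until relapse or death from any cause, whichever comes first for subjects who achieve CRc". EFS runs "until the date of documented relapse after CR, treatment failure or death from any cause, whichever occurs first". Neither definition stops counting at end of treatment, at transplant or at the last assessment.

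**Censoring (SAP 6.1.3).** For RFS, "RFS is censored on the date of last relapse-free disease assessment date". The clarification that follows, "Last relapse-free disease assessment date refers to the" last disease assessment of the subject, adds nothing about which contacts qualify. The EFS rule reads: "For a subject with none of these events, EFS is censored at the date of last disease assessment".

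**Data after treatment (SAP 3.2, Phase 2 part).** After the 30-day safety visit, subjects enter the "long-term follow-up period for collection of subsequent AML treatment, remission status, relapse and survival (cause and date of death"). This lasts at least until 3 years after the last subject's first treatment.

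**What an assessment is.** SAP 6.1.1 states: "Antitumor response will be assessed on the days of bone marrow sampling". SAP 7.4 uses the term disease assessment for the evaluation at which a transfusion-independent CR is judged. No section defines the term for censoring.

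**Estimator (SAP 7.4).** Time-to-event variables are summarised by Kaplan-Meier curves and medians with 95% CIs.

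**The concern.** Kaplan-Meier requires that leaving the risk set carry no information about what happens next. Take two subjects in remission with the same last marrow date, both followed afterwards. If one dies a year later, that subject stays at risk for the whole year and contributes an event. If the other is still in remission, that subject is removed at the marrow date. Which rule applies depends on the future outcome.

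The SAP does better elsewhere. OS (6.1.3) and the cumulative incidence of death (6.1.4) are censored at the date last known alive, which matches how deaths are found. Duration of CR (6.1.3) has its own transplant censoring rule. RFS and EFS have neither.

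At stake are the curves and medians for two secondary efficacy endpoints. On the marrow-based reading they would depend on how long marrow sampling continued and on how many subjects left the study for transplant. On the other reading they would not. Two programmers could derive different curves from the same data.

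**Working it through.** **The plan's own figures.** The SAP gives no figure for RFS or EFS, so there is nothing to reproduce for them. Its one design figure, power above 80% for CR with 70 subjects (55% against 70%, one-sided 0.05), does reproduce: at least 46 responders are needed, exact alpha is 0.0452 and power is 0.820. This concern does not touch it.

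**Mechanism.** Suppose that after marrow sampling stops, E subjects will have an event during follow-up and W will stay well. At the next event a common basis gives a hazard increment of 1/(E + W). If the W subjects have already been censored, the increment is 1/E, which is always larger. The curve therefore falls too fast.

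**Simulation A.** Inputs, all assumed and none in the SAP:
- 65 subjects in CRc; relapse 0.018/month; death in remission 0.005/month; mean 8 months from relapse to death.
- Off-study HSCT subjects have their last marrow at month 4. Others stop sampling at 0.02/month, or by month 24.
- Follow-up is 30 to 42 months.

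True 24-month RFS is exp(-(0.018 + 0.005) x 24) = exp(-0.552) = 57.6% (57.5% simulated). If follow-up contacts are not disease assessments:

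| Off-study HSCT | All late events captured | Gap (points) | Late deaths only, no late relapses | Gap (points) |
|---|---|---|---|---|
| 0% | 52.7% | 4.8 | 55.0% | 2.5 |
| 20% | 49.1% | 8.4 | 52.3% | 5.2 |
| 40% | 45.2% | 12.3 | 49.7% | 7.8 |
| 60% | 40.0% | 17.5 | 46.1% | 11.4 |

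A separate run of the same model gave 57.4% true against 52.5, 49.2, 45.0 and 40.2%, a largest gap of 17.2 points. When follow-up contacts counted as assessments it gave 57.4% against 57.4%.

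**Simulation B.** This uses a different set of assumptions: exponential RFS; follow-up 36 to 54 months; last on-study assessment exponential with mean 6, 12 or 24 months, capped at 26 cycles of 28 days (728 days); 70% of events are relapses; 400,000 subjects. Estimated 24-month RFS:

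| True value | Mean 6 months | Mean 12 months | Mean 24 months |
|---|---|---|---|
| 50% | 34.5% | 38.8% | 43.2% |
| 60% | 40.2% | 46.2% | 52.1% |
| 70% | 46.2% | 54.2% | 61.6% |

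- With a true value of 60% and only non-relapse deaths captured late, the estimates are 44.8%, 53.0% and 56.9%.
- If everyone is assessed up to the cap, there is no bias at 24 months, but 36-month RFS reads 22% against 47%.
- If 3-monthly remission-status contacts count as assessments (interval assumed), the result is 60.0% against 60.0%.

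**EFS.** No simulation was run. From the rules in 6.1.3:
- *Downward:* the mechanism above; and event-free subjects with no post-treatment assessment are censored at treatment start, while deaths among such subjects still count.
- *Upward:* treatment failure is dated at end of treatment; and relapse counts only after CR although failure is judged on CRc, so relapse after CRp or CRi is not an event.

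The net sign cannot be derived from the text.

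**The case against.** The strongest reply is that the SAP does not exclude follow-up contacts. Section 6.1.1 ties antitumor response to marrow days but does not define disease assessment. Relapse in the same section can be declared on peripheral blasts or extramedullary disease without a marrow. Section 3.2 collects remission status in long-term follow-up, and a record of continued remission can fairly be read as a relapse-free assessment. On that reading the bias disappears. **This stands:** the bias is conditional. It does not remove the point, because the usage in 6.1.1 and 7.4 leans towards the marrow-based meaning and nothing in the SAP settles it.

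A reader might infer that both curves are biased downward as the plan is written. The SAP does not support that. For RFS it depends on the undefined term; for EFS, opposing rules leave the net direction open.

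The sizes can also be challenged. Every hazard, stopping time and transplant share is assumed. The SAP provides for transplant without leaving the study, and gives no basis for a 40 to 60% off-study share. With no off-study transplant the gap is 4.8 points, below one standard error of the estimate: sqrt(0.575 x 0.425 / 65) = 6.1 points at least. **This stands as a caution on size.** A systematic shift of that order is still avoidable, and it does not shrink with more subjects.

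Finally, the endpoints are untested and any RFS bias runs against the regimen, so it cannot create a false efficacy claim. That is correct and limits the severity.

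**Conclusion.** The point holds in conditional form. Late events and censoring rest on different bases unless long-term follow-up remission-status contacts count as disease assessments, which the SAP does not say. If they do not count, Kaplan-Meier RFS is biased downward; if they do, the bias is about zero. Under Simulation A, 24-month RFS reads roughly 0 to 17 points low: 0 where contacts count, about 5 with no off-study transplant, contacts not counted and all late events captured, and about 17 with 60% transplanted off study. Simulation B gives gaps of about 7 to 24 points when contacts do not count (for example 70.1 - 46.2 = 23.9, using the simulated true value), which shows how far the size depends on when marrow sampling stops. None of these inputs comes from the SAP, so the figures illustrate the effect and do not predict it. RFS and EFS are secondary and descriptive, and the primary CR conclusion is unaffected. The change should be made, but it does not threaten the trial's main result.

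**What to change.** In SAP 6.1.3, put events and censoring on one basis. Censor RFS and EFS at the latest date on which the subject is documented alive and relapse-free, and state explicitly that remission-status contacts in long-term follow-up qualify.

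Add a sensitivity analysis that counts neither events nor event-free time after the last on-study marrow assessment. It is symmetric, and it is unbiased in Simulation A, where stopping of marrow sampling is unrelated to prognosis. That condition may not hold in practice, which is why it belongs as a sensitivity analysis.

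The cost is a few sentences in the SAP and one derived date from data that section 3.2 already collects. The drawback is that remission status at a follow-up contact is less rigorous than a marrow assessment, so some early relapses may be dated late; the sensitivity analysis helps to show whether this matters.

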If bone marrow myeloblasts between 5% and 25% and a decrease from baseline of at least 50% in the marrow myeloblasts, no detectable (or trace of residual) blasts, and no evidence of extramedullary leukemia, the response is classified as PR.

Not Evaluable (NE)/No Response (NR):

In the situation where no bone marrow assessments are performed or myeloblast value is missing, blast value from peripheral blood is missing or $\leq 2\%$, and extramedullary leukemia is missing or not done, the response will be classified as NE. In any case response cannot be categorized as CR, CRp, CRi, PR or NE, it will be categorized as NR.

Relapse:

Relapse after CR, CRh, CRp or CRi is defined as a reappearance of leukemic blasts in the peripheral blood ($>2\%$) or $\geq 5\%$ myeloblasts in the bone marrow not attributable to any other cause or reappearance or new appearance of extramedullary leukemia.

Relapse after PR is similarly defined with reappearance of significant numbers of peripheral blasts and an increase in the percentage of myeloblasts in the bone marrow to $> 25\%$ or $>2\%$ blast in peripheral blood not attributable to any other cause or reappearance or new appearance of extramedullary leukemia.

Best Response:

Best response is defined as the best measured response to treatment for all visits (in the order of CR, CRp, CRi, PR, NR and NE) post-baseline. Subjects who achieve the best responses of CR, CRp, CRi, or PR will be classified as responders. Subjects who do not achieve at least PR will be classified as non-responders.

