Defined as the time from the date of start date of the treatment until the date of having a neutrophil count of $\geq 1,000/\text{mm}^3$ and platelet count of $\geq 100,000/\text{mm}^3$. Subjects with none of these events are censored at the date of last assessment within each treatment cycle.

- MRD

MRD is defined as binary endpoint, negative or positive. More detail of the definition is in Section 6.5. MRD rate is defined as the percentage of subjects whose MRD is negative.

- MR

MR is defined as binary endpoint, MR or no MR. More detail of the definition is in Section 6.5. MR rate is defined as the percentage of subjects who achieve MR.

- MRD-negative CR rate after induction

Defined as the number of subjects who achieve the best response of CR and whose MRD is negative during induction period divided by the number of subjects in the analysis population during induction therapy period. Subjects with unknown or missing response, or who provide no information on response will be treated as non-responders and will be included in the denominator when calculating rates.

- Overall MRD-negative CR rate for any treatment period

Defined as the number of subjects who achieve the best response of CR and at least one post-baseline MRD is negative divided by the number of subjects in the analysis population. If subjects have multiple MRD samples collected across different timepoints, the overall MRD status is negative if there is at least one MRD sample is negative and the overall MRD status is positive if all available MRD samples are positive. Subjects with unknown or missing post-baseline MRD status, or who provide no information on post-baseline MRD status will be treated as MRD positive and will be included in the denominator when calculating rates.

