6.5 Other Variables

- FLT3-ITD mutation status
- FLT3-TKD mutation status
- FLT3 mutation status

Either of FLT3-ITD mutation status or FLT3-TKD mutation status is positive, this variable shows positive.

- MRD

MRD negative is defined as summed FLT3-ITD signal ratio of any post-baseline sample $\leq 10^{-4}$. MRD positive is defined as summed FLT3-ITD signal ratio of any post-baseline sample $> 10^{-4}$.

- MR
MR is defined as summed FLT3-ITD signal ratio of any post-baseline sample $\leq 10^{-2}$.
No MR is defined as summed FLT3-ITD signal ratio of any post-baseline sample $> 10^{-2}$.
- FLT3-ITD signal ratio
FLT3-ITD signal ratio is defined as the ratio of FLT3-ITD sequence reads divided by the total number of FLT3 sequence reads. This is being calculated by central laboratory. For subjects with more than one FLT3-ITD variant, the FLT3-ITD signal ratio will be summed at each timepoint.
- Duration of exposure (days)
Duration of exposure to each treatment will be calculated in days, using the following formula:
 - Duration of exposure for each treatment cycle is defined as Last dose date – First dose date + 1 – (on-study HSCT period for subjects undergo on-study HSCT) for each cycle. For Phase1 part, last dose date of study drug exposure = (initial dose date of the cycle + 14 – 1) if last dose date of the cycle is not captured on dosing CRF.
 - Duration of exposure for each treatment period is calculated as sum of the duration of exposure for each treatment cycle.
 - Duration of exposure during study for study drug =
(Duration of exposure for Induction period) + (Duration of exposure for Consolidation period) + (Duration of exposure for Maintenance period).When the last date of exposure is beyond cutoff date, the cutoff date will be used as the last date of exposure. When the start or stop date is missing, then the exposure will be treated as missing.
- Number of dosing days (days)
Defined as number of days with non-zero dosing.
Number of dosing days is calculated for each treatment period.
- Cumulative dose (mg or g)
Defined as total amount of drug given to a patient, which calculated as follows:
 - ASP2215: Sum of (actual dose level * number of dosing days within each dose level)
 - Chemotherapy: Sum of actual dose across the days when administered.
Actual dose is calculated as:
(Actual volume administered / Total volume prepared)* Intended dose * Body surface area.

If number of doses taken is unknown, it will be treated as missing.

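### None of the three CR-with-MRD rates requires the MRD-negative sample to be taken while the subject is in CR, and the rule for mixed samples is left open for two of them

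*SAP*

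**What the plan says.** Three Phase 2 endpoints in the SAP combine CR with MRD.

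- **Secondary CR rate without MRD (6.1.3).** The responder rule is "Responders achieve that the best response is CR and MRD status is negative". The endpoint is modelled on the secondary CR rate, whose count of CRs is "divided by the number of subjects in the analysis population after each treatment therapy period".
- **Exploratory induction rate (6.1.4).** It counts subjects who "achieve the best response of CR and whose MRD is negative during induction period".
- **Exploratory overall rate (6.1.4).** It counts subjects who "achieve the best response of CR and at least one post-baseline MRD is negative". A further sentence pools the samples: one negative sample makes the subject negative overall, and only a subject whose available samples are all positive is positive.

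Two definitions feed these rates. In 6.1.1, "Best response is defined as the best measured response to treatment for all visits". In 6.5, "MRD negative is defined as summed FLT3-ITD signal ratio of any post-baseline sample" at or below 10^-4, while "MRD positive is defined as summed FLT3-ITD signal ratio of any post-baseline sample" above 10^-4.

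Section 7.4 leaves response assessments after HSCT out of the main response analysis and brings them back in a sensitivity analysis. It does not say whether MRD samples are treated the same way.

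**The concern.** A rate of CR without MRD is read as the share of subjects in remission with no measurable residual disease. That requires both facts to be true of the same subject at the same time. The SAP derives them separately, as a best response over visits and an MRD status over samples, and joins them with no condition on their dates. A subject who is MRD negative while in CRi, and who later reaches CR with a positive sample, was never in MRD-negative CR but can be counted as if he or she had been.

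A second weakness sits beside this one. The words that define MRD negative and MRD positive in 6.5 overlap for anyone with both kinds of sample. For the secondary and induction rates nothing resolves the overlap, so two programmers could report different values from the same data.

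**Working it through.** **The plan's own figure.** The SAP gives no expected MRD rate and no size for the MRD analysis set. Its only design figure is the power of the primary CR test in 4.1.2: n = 70, 55% against 70%, one-sided 0.05, power above 80%. With X binomial, the smallest r with P(X ≥ r | 70, 0.55) ≤ 0.05 is r = 46 (46/70 = 65.7%). Then P(X ≥ 46 | 0.55) = 0.0452 and P(X ≥ 46 | 0.70) = 0.820. The statement is reproduced, and no MRD result enters it.

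**The definitions side by side.**

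| Rate | Limits the MRD sample to a period? | Requires the sample during CR? | Rule for mixed samples? |
|---|---|---|---|
| Secondary, per period | Implied, not stated | No | No |
| Exploratory induction | Yes, induction | No | No |
| Exploratory overall | No, by design | No | Yes, one negative suffices |

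**Four constructed subjects.** For the per-period rates, best response is taken within the period reported.

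| Subject | Samples in time order | CR and negative together? | Overall rate | Secondary, after induction | Exploratory induction |
|---|---|---|---|---|---|
| A | Induction: CRi, negative. Consolidation: CR, positive | Never | Counted | Not counted | Not counted |
| B | Induction: CR, positive. Maintenance: CR, negative | In maintenance | Counted | Not counted if the period limits the sample; otherwise undetermined | Not counted |
| C | Induction: CRi, negative, then CR, positive | Never | Counted | Undetermined | Undetermined |
| D | Induction: no CR, positive, then CR, negative | In induction | Counted | Undetermined | Undetermined |

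Undetermined means that the subject meets the words of both the negative and the positive definition in 6.5.

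**Direction, overall rate.** Let S be the subjects with at least one negative sample taken in CR, and T those with best response CR and at least one negative sample at any time. Every member of S is in T. Hence |T|/N ≥ |S|/N, and the excess is the number of subjects like A and C divided by N. The error is upward or zero.

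**Direction, secondary rate.** If one negative sample suffices, C is wrongly counted and the rate rises. If a positive sample prevails, D is wrongly excluded and the rate falls. The text does not choose, so the direction is open. The same holds for the induction rate.

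**Size.** Each misclassified subject moves a rate by 100/N percentage points. The planned Phase 2 enrolment of about 80 (4.1.1) gives 100/80 = 1.25. Section 7.4 assigns MRD analyses to the MRD analysis set, which is limited to FLT3-ITD-positive subjects with baseline and post-baseline MRD data. Its size is not given. Assuming 50 gives 2.0 and assuming 40 gives 2.5. Three such subjects would move the rate by 3.75 points (N = 80) to 7.5 points (N = 40). The count of three is for illustration only.

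**The case against.** The strongest reply is that a reader could make too much of this.

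- **That no endpoint ties MRD to a treatment period.** The documents do not support this. The exploratory induction rate names the induction period for MRD. The secondary rate is built on a per-period CR rate, and the natural reading carries that period over to the MRD condition. On that reading, the worry that a negative maintenance sample is credited to induction (subject B) does not arise, and the two induction rates are closer to duplicates than to a contradiction. What remains is that the limit is implied rather than written.
- **That all three rates are biased upward.** This needs the one-negative-suffices rule, which the SAP states only for the overall rate. Section 6.5 can be read as a classification of each single sample, which fits its summing of variants at each timepoint. Under that reading the secondary rate has no multiple-sample rule at all.
- **The overall rate is meant to pool periods.** Its title and pooling rule show this. Pooling periods does not, however, explain pairing a CR with a negative sample taken outside CR.
- **Unpaired results may be rare.** The SAP leaves the assessment schedule to the protocol (section 2). If MRD is drawn only with the response marrow, and once per period, subjects C and D cannot occur within a period. Subject A still can across periods.
- **The rates are descriptive.** They carry 95% confidence intervals and no test. This stands, and it limits the consequence.

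**Conclusion.** The concern holds in this form. No CR-with-MRD endpoint requires the negative sample to fall within CR. For the exploratory overall rate this follows from a stated rule, and the rate can only equal or exceed the one obtained from the same samples with CR required. For the secondary rate, the period limit on the MRD sample is implied, the mixed-sample rule is missing, and the error could go either way. The exploratory induction rate has the period but not the link to the CR assessment.

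The effect is 1.25 to 2.5 points per misclassified subject, for assumed denominators of 80 to 40. How many subjects would be affected cannot be derived from the SAP. A reader might infer that the trial's main conclusion is at risk. It is not, because the primary CR rate, its comparison with 55% and the sample size do not use MRD.

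**What to change.** Change 6.1.3, 6.1.4 and 6.5 as follows.

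1. In 6.5, classify MRD for each sample as negative or positive by the 10^-4 cut-off, and state one rule for a subject with several samples.
2. For per-period rates, require CR in that period and a negative sample from the CR assessment, or from the same period while CR persists.
3. For the overall rate, require at least one negative sample on or after first CR and before relapse.
4. Treat MRD samples taken after HSCT as 7.4 treats response data: out of the main analysis and in the sensitivity analysis.
5. Align the exploratory induction rate with the secondary rate after induction, or drop one of them.

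The cost is SAP wording and programming, and the reported rates may come out lower.
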